5.1 Inclusion Criteria

2 Year Primary Study

Subjects must meet all the following characteristics for inclusion in the study.

- Subject is at least 21 years of age
- Subject is skeletally mature
- Subject requires primary, unilateral total hip arthroplasty, due to degenerative joint disease
- Subject has a preoperative Harris Hip Score of ≤ 70
- Subject has met an acceptable preoperative medical clearance and is free or treated for cardiac, pulmonary, hematological, or other conditions that would pose excessive operative risk
- Subject has given consent to participate in the study after the nature, scope and possible consequences of the study have been explained in an understandable form
- Subject is able to fully understand the purpose of the study, his/her role as a participant in the study, and plans to be available through two years post-operative follow-up

10 Year Extension Study

- Subject has completed the 2 year primary study

- Subject has signed an Independent Ethics Committee (IEC) approved Informed Consent Form agreeing to participate in the extension study after the nature, scope and possible consequences of the study have been explained in an understandable form
- Subject is able to fully understand the purpose of the study, his/her role as a participant in the study, and plans to be available through ten years post-operative follow-up

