5.2 Exclusion Criteria

2 Year Primary Study

Subjects with any of the following characteristics must be excluded from participation in the study.

- Subjects with diagnosis known to be of high risk for failure of THA
- Subject requires bilateral THR
- Subject requires revision of a prior hip replacement
- Subject has active infection or sepsis (treated or untreated)
- Subject has history of local hip infection
- Subject has presence of known metastatic or neoplastic disease
- Subject has conditions that may interfere with the THA survival or outcome (e.g. , Paget's or Charcot's disease, vascular insufficiency, muscular atrophy, uncontrolled diabetes, or neuromuscular disease)
- Subject has need for structural bone grafts to support the implant
- Subject has contralateral lower extremity condition causing abnormal ambulation and noncompliance with rehabilitation
- Subject has other joint replacements, or plans for other joint replacement surgeries in the next 2 years
- Subject has had systemic steroid therapy within 3 months prior to surgery
- Subject has life expectancy less than 2 years
- Subject has had drug therapy for the index hip with intra-articular corticosteroid therapy or intra-articular hyaluronic acid therapy (or any other intra-articular therapy) within 6 months of enrollment into the study
- Female subject of child-bearing age not using an approved method of contraception
- Subject has inadequate bone stock to support the device (severe osteopenia, family history of severe osteoporosis or osteopenia)
- Subject has known moderate to severe renal insufficiency
- Subject has an emotional or neurological condition that would pre-empt their ability or unwillingness to participate in the study including mental illness, mental retardation, or drug, alcohol abuse
- Subject is severely overweight (BMI>40)
- Above knee amputation of the contralateral and or ipsilateral leg
- Known allergies to any components of the devices
- Subject is entered in another investigational drug, biologic, or device study

- Subject is a prisoner

10 Year Extension Study

- In the opinion of the surgeon, the subject's health, safety or well-being may be compromised or harmed by continuation in the extension phase or participation may not be in the subject's best interests.

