14.0 Post-operative Procedures

Subjects will be seen post-operatively at the 3 month, 6 month, 1, 2, 5, 7 and 10 year intervals, post-surgery. At the discretion of the Sponsor, additional unscheduled follow-up visits may be performed. Information regarding interval specific study events may be found in the Study Events Schedule.

Post-operative procedures include:

- Revision status
- Assessment of adverse events
- Collection of whole blood samples for metal ion analysis at the 3 month, 6 month, 1, 2, 5, 7 and 10 year intervals.
- Telephonic assessment of adverse events at 6, 8 and 9 year intervals.
- A clinical evaluation will be completed by the Investigator for purposes of completing the HHS for investigational subjects at the 3 month, 6 month, 1 and 2 year intervals. Any HHS data available for control subjects will be collected retrospectively up until 2 years post-op. From the 5 year interval onwards (5,7 and 10 year intervals) HHS will be collected prospectively for all subjects.
- AP and lateral radiographs will be obtained. Copies will be provided to the Sponsor for the purpose of obtaining independent radiographic analysis for investigational subjects. Any radiographic data available for control subjects will be collected retrospectively up until 2 years post-op. From the 5 year interval onwards all

radiographic data will be collected prospectively.

- Completion of HOOS subject questionnaire for investigational subjects at the 3 month, 6 month, 1 and 2 year intervals Any HOOS data available for control subjects will be collected retrospectively up until 2 years post-op. From the 5 year interval onwards (5,7 and 10 year intervals) HOOS will be collected prospectively for all subjects.

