18.0 Device Failure leading to revision

In the short term, THA failure can occur due to infection, dislocation, instability, and/or subject experiencing severe pain due to various causes. Reduced mobility alone, is typically not a predominant factor in prompting revision surgery. In the longer-term, aseptic loosening and/or severe pain may become a determining factor as to whether to proceed with device revision. Reasons for removal are not limited to these circumstances alone.

The Sponsor should be notified immediately when a revision is planned. The Sponsor or its designee will provide an explant retrieval kit and the site will return any revised components for retrieval analysis according to provided instructions. Any explanted devices must be logged on the device accountability log when explanted and shipped to the Sponsor or its designee. Blood will be collected for metal ion analysis and radiographs taken prior to the revision procedure as per an unscheduled visit on the study visit schedule. Patients who have undergone revision surgery will be withdrawn from the study and no additional follow-up visits will occur.

Explanted components are to be sterilized by steam autoclave or other appropriate sterilization method according to the Institution's standard sterilization procedures. Only properly packaged explants should be shipped, and the Sponsor notified before any shipment. If possible, the Sponsor will collect histological (bony in-growth quality, bone quality, response to potential wear debris, etc.) and metallurgical (metal wear, deformation, cracking, corrosion, etc.) information from explants, and this information will be reported in annual safety reports. For all explants, the Investigator must record and forward a description of intra-operative findings including: 1) presence of wear debris, 2) what types of components are being replaced, 3) and intraoperative findings relating to the device failure. It should be noted that the Sponsor is not always able to retrieve known explants.

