## 5. Statistical Considerations

### 5.1 Determination of Sample Size

A total of 25 subjects were enrolled in the study (20: ODH-ODH and 5 controls). All patients completing the 2 year primary follow up were invited to participate in the extension phase of the study. No justification for the sample size was provided.

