### 6.9.1 Device-Related Revisions

The Kaplan-Meier product limit survival estimates will be presented at 6-months, 2-years, 5-years, 7-years and 10-years post-op along with the associated 95% confidence intervals. The event of interest will be device-related revisions. Subjects who do not have device-related revision will be censored either at the time-point being analysed i.e. 5-years at the 5-year interim analysis etc. or at the time they discontinue from the study for

Statistical Analysis Plan	
A Consecutive Series Pilot Study Evaluating the Safety and Effectiveness of a New Hard-on-Hard Total Hip Replacement System in Patients with Non-inflammatory Arthritis with a Standard THA Metal Ion Control Group	Number: 2011-ODHH166
	ST: 1040
	Version: V1.0 26-Nov-2018
	Page: 11 of 13

any other reason i.e. lost to follow-up. This analysis will be presented by treatment (control/ R3 ODH-ODH).

The Kaplan Meier Survival plot will also be presented at 12 months both overall and by device type.

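### Revisions between the 2-year exit and the 5-year re-consent are not collected for subjects who stay out, and the censoring wording can count those years as event-free, so 5- to 10-year implant survival may be overstated

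*SAP*

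**What the plan says.** **Follow-up.** Protocol 2.0 gives the primary study two years of follow-up and makes the extension subject to an updated consent. In the Study Events Schedule the 2-year window is days 689 to 773 and the next column is the 5-year visit, days 1812 to 2006, where eligibility and consent are ticked again. Calls come later: "Telephonic assessment of adverse events at 6, 8 and 9 year intervals" (Protocol 14.0).

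**Re-entry.** Apart from consent and availability, Protocol 5.1 asks only that "Subject has completed the 2 year primary study". The only extension exclusion in 5.2 is the surgeon's judgement: "In the opinion of the surgeon, the subject's health, safety or well-being may be compromised or harmed by continuation in the extension phase", or that taking part is not in the subject's best interests. Protocol 18.0 adds: "Patients who have undergone revision surgery will be withdrawn from the study and no additional follow-up visits will occur".

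**Retrospective collection.** Protocol 2.0 and 14.0 provide it for the original control group, with clinical and radiographic data up to 2 years. There is no such route for investigational subjects.

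**Analysis.** SAP 6.9.1 plans Kaplan-Meier estimates at 6 months and 2, 5, 7 and 10 years by treatment, in the safety population (everyone enrolled and treated, SAP 6.2). "Subjects who do not have device-related revision will be censored either at the time-point being analysed", or when they discontinue for another reason. SAP 6.4 censors lost, deceased and withdrawn subjects on the date of that event, and everyone else at the end-of-study visit or the interim analysis date. On the plot: "The Kaplan Meier Survival plot will also be presented at 12 months both overall and by device type".

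**The concern.** Device-related revision is a primary endpoint, and long-term safety is the stated purpose of the extension. The 5-, 7- and 10-year estimates are presented as survival from surgery. Between years 2 and 5, however, whether a revision enters the data depends on whether the subject comes back, and a revised subject may be less likely to come back, or may be treated as withdrawn under Protocol 18.0.

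Two errors are possible. A gap revision in a subject who stays out is never recorded. And a subject who stays out may be kept in the risk set as event-free through years in which nobody observed them. The planned confidence interval reflects neither, and a curve at 12 months cannot show the break.

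**Working it through.** **1. The plan's own figures.** No survival rate, revision rate or power is stated; SAP 5.1 says of the 25 subjects: "No justification for the sample size was provided". The visit windows can be reproduced:
- 2 years: 2 × 365.25 = 730.5, rounded up to 731; ± 42 days gives 689 to 773.
- 5 years: 5 × 365.25 = 1826; −14 and +180 days give 1812 to 2006.

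Time without scheduled contact: 1812 − 773 = 1,039 days (2.84 years) at least, and 2006 − 689 = 1,317 days (3.61 years) at most.

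**2. Where a non-entering 2-year completer is censored.** Such a subject has missed no scheduled visit, so is not lost to follow-up under Protocol 16.0, and need not be dead or withdrawn. SAP 6.4 then offers two dates, end-of-study visit or interim analysis, without choosing. The schedule ticks the End of Study form only at year 10, unless completed earlier. SAP 6.9.1 offers the analysed time-point or discontinuation. Both 2 years and 5, 7 or 10 years are possible readings.

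**3. Size per missed revision.** Assume 20 investigational hips event-free at 2 years and k revised in the gap, none captured. True 5-year survival is (20 − k)/20 and the planned estimate is 100%, so the error is k/20, or 5 points each (k = 1: 95% against 100%; k = 2: 90% against 100%). With 5 controls the same arithmetic gives 1/5, or 20 points each.

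**4. Worked example (assumed).** Of 20 hips, 2 are revised in the gap, 3 unrevised subjects decline, 15 unrevised subjects enter, and 1 of these is revised in year 6.

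| Case | 5 years | 10 years |
|---|---|---|
| Truth | 18/20 = 90% | 0.90 × 17/18 = 85% |
| Gap-revised stay out; non-entrants censored at 2 years | 100% | 14/15 = 93.3% |
| Gap-revised stay out; non-entrants censored at the nominal time-point | 100% | 19/20 = 95% |
| Both gap-revised enter and are recorded; 3 decliners censored at 2 years | 15/17 = 88.2% | 15/17 × 14/15 = 82.4% |

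**5. Dependence on who re-enters.** Simulation of 20,000 trials of 20 hips with a constant revision hazard, 80% of unrevised subjects re-entering and non-entrants censored at 2 years. Hazards and re-entry shares are assumptions; the documents give none. Cells show survival at 5 / 10 years.

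| Share of gap-revised who re-enter | Hazard 1% per year | Hazard 2% per year |
|---|---|---|
| Truth | 95.1% / 90.5% | 90.5% / 81.9% |
| 0% | 98.0% / 93.2% | 96.1% / 87.1% |
| 50% | 96.2% / 91.5% | 92.5% / 83.7% |
| 80% (same as unrevised) | 95.2% / 90.5% | 90.5% / 81.9% |
| 100% | 94.4% / 89.8% | 89.1% / 80.6% |

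The 5-year error runs from about +3 points (1% hazard) or +6 points (2% hazard), through zero, to about −1 point.

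**6. Sampling error for scale.** The exact 95% upper limit on the revision proportion is 1 − 0.025^(1/20) = 16.8% for 0/20, and 52.2% for 0/5. At 1% per year the chance of no gap revision in 20 hips is exp(−0.03 × 20) = 55%.

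**The case against.** A reader might infer that the curve must be flat from 2 to 5 years by construction and that long-term survival is certainly overstated. The documents do not support that:
- Revision is not an extension exclusion. The Protocol Summary and SAP 5.1 say that all 2-year completers are invited.
- Protocol 14.0 lists revision status and adverse events among the post-operative procedures, with a visit at year 5. Protocol 17.1 provides a revision form, and SAP 6.3 carries a revision forward. A gap revision in a subject who re-enters can therefore be recorded.
- Applying Protocol 18.0 as a bar to entry is an inference. Its withdrawal rule does no harm once a device-related revision has been captured, because that revision is the survival event.
- The direction of bias depends on who re-enters, as steps 4 and 5 show.

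It is also fair that SAP 6.9.1 allows censoring at discontinuation, that censoring a decliner at exit is the more natural reading, and that SAP 6.6 reports attendance by visit. This is a small descriptive pilot with no success threshold, and a flat stretch would be common by chance.

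All of that stands, and it limits the claim to what may happen. It does not supply a source of revision data for subjects who stay out, a rule for gap-revised subjects, or a single censoring date. Protocol 22.3.1 moreover describes the extension as those who completed the 5-, 7- and 10-year visits, which a subject withdrawn after a gap revision could not do.

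**Conclusion.** The concern holds as a risk of overstatement. The plan can be followed as written and still miss gap revisions in non-entrants and credit unobserved years as event-free. The error at 5 years is up to 5 points per missed revision among 20 hips, assuming all 20 are event-free at 2 years. At assumed hazards of 1% to 2% per year it averages about 3 to 6 points if no gap-revised subject re-enters. It is zero if revised and unrevised subjects re-enter equally and the revisions are recorded, and about 1 point the other way if all revised subjects re-enter against 80% of the others.

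This should be fixed, but it is not critical: with 20 hips and descriptive survival, sampling error is larger than the likely bias. The reason to act is that the confidence interval does not include this bias, and a single missed event turns 95% into 100%.

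**What to change.** 1. **Ascertainment (Protocol 5.1, 18.0 and schedule).** At the 5-year time-point, obtain revision status with date, and vital status, for all 25 original subjects who consent, whether or not they join the extension. Extend the existing retrospective-consent route to investigational subjects and to 5 years. Count a device-related gap revision as an event on its date. Reconcile 5.1 with 18.0 so that it is clear whether a subject revised in the gap may enter.
2. **Censoring (SAP 6.4 and 6.9.1).** Censor every event-free subject at the last date on which revision status is known. For a non-entrant whose status is not ascertained, that is the 2-year visit, never a later nominal time-point.
3. **Sensitivity analysis.** If ascertainment is incomplete, let extension subjects contribute from surgery to the 2-year visit and re-enter the risk set at the extension-consent date. Nobody is then at risk in between, so report 2-year survival and, separately, later survival labelled as conditional on reaching re-consent unrevised.
4. **Display (SAP 6.9.1).** Draw the curve by device to the time-point analysed, with numbers at risk, instead of at 12 months.

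**Cost.** A consent amendment with ethics approval, one chart look-up for at most 25 subjects, which some may refuse, and a few lines in the SAP. Reported survival may come out lower.

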#### 6.9.2 Adverse Events

The total number of adverse events of all classifications will be summarised by treatment and overall along with the number and proportion of subjects experiencing an adverse event of any type.

The above will also be summarised by seriousness, severity, relationship to study device/ procedure and outcome.

The frequency of ADEs and SADEs that occurred between each study visit will be presented along with the total for the overall study. The number of subjects recording each will also be presented.

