2.0 Study Summary

2 Year Primary Study

- The purpose of the investigation is to assess the early safety and efficacy of R3 ODH-ODH utilization during primary THR.
- This is a prospective, consecutive series, non-randomized, multi-center clinical study.
- Twenty (20) patients are to be enrolled in the current study, with 5 THA control subjects for metal ion analysis.
- This study is to be executed according to ICH GCP guidelines for clinical trials and in accordance with the Declaration of Helsinki.
- Patients will be followed-up for two (2) years post-operatively.
- Interim analyses will be conducted post-operatively at six (6) months and a full study report will be generated at two (2) years.

10 Year Extension Study

- The purpose of the additional follow-up through 10 years post-implantation is to assess the long term safety and efficacy of R3 ODH-ODH utilization during primary THR.

- Both investigational and control subjects will be invited to participate and sign an updated Informed Consent Form if agreeable.
- Subjects from the original control group will be invited to participate in retrospective collection of secondary endpoint data as this was not originally collected in the 2 year primary study. This data includes adverse event data, radiography, HOOS, HHS, demographic and medical history data if available. If agreeable, they will be asked to provide written Informed Consent.
- Control subjects who do not wish to participate in the extension phase may still consent to the retrospective data collection from their medical files. Similarly, control subjects who do not wish to consent to the retrospective collection of data from their medical files may still participate in the extension phase of the study.
- This extension study is to be executed according to ICH GCP guidelines for clinical trials and in accordance with the Declaration of Helsinki.
- Subjects will be followed for 10 years post-operatively.
- Interim analyses will be conducted post-operatively after all subjects have completed 5 year and 7 years visits. A complete study report will be completed when all subjects have completed the 10 year follow-up.

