22.3 Statistical Analysis

22.3.1 Analysis of Population

2 years Primary Study Analysis

The primary analysis will be comprised of all patients who have completed the 6 month post-operative follow-up visit. Twenty-Five patients who have completed the 6 month visit are needed to complete the primary interim analysis and the metal ion analysis will compare to control subjects. A final analysis which will include efficacy assessments will be completed at the 2 year time point. All subjects who do not complete the study, for reasons other than device failure, will be described in the final analysis.

The control subjects will ONLY be asked for blood samples and no other study assessments will be required. Therefore, they will not be included in the over-all analysis. The metal ion results of the five control subjects will be compared to those

of the 20 ODH subjects in order to validate the metal ion levels in the ODH population.

5, 7 and 10 year Study Analyses

The extension study will be comprised of all subjects who have completed the 5 year, 7 year and 10 year post-operative follow-up visits. The analyses will include the descriptive statistics in both safety and efficacy variables. All the data collected during the study will be presented as tables or listing.

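### SAP 6.9.2 tabulates prospectively collected ODH adverse events alongside chart-review control events with no denominator rule, so the control and pooled proportions are likely understated

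*SAP*

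**What the plan says.** SAP 6.9 assigns all primary endpoints to the safety population. SAP 6.2 defines that population by enrolment and receipt of study treatment, with no condition on adverse event data being available. SAP 6.9.2 then says: "The total number of adverse events of all classifications will be summarised by treatment and overall". It adds the number and proportion of subjects with an event, and breakdowns by seriousness, severity, relationship and outcome. Its only table by interval is narrower: "The frequency of ADEs and SADEs that occurred between each study visit will be presented".

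On how control data arose, protocol 22.3.1 says of the 2-year study: "The control subjects will ONLY be asked for blood samples and no other study assessments will be required". It continues: "Therefore, they will not be included in the over-all analysis". For the extension, protocol 2.0 plans "retrospective collection of secondary endpoint data as this was not originally collected in the 2 year primary study" and specifies: "This data includes adverse event data, radiography, HOOS, HHS, demographic and medical history data if available". Consent to chart review is separate from consent to the extension: "control subjects who do not wish to consent to the retrospective collection of data from their medical files may still participate in the extension". The reverse choice, chart review without the extension, is also allowed.

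For ODH subjects, protocol 11.0 and 17.0 collect operative complications at the time of surgery. Protocol 17.2 requires specific questioning about adverse events at each contact.

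**The concern.** A proportion in a safety table is read as events among people who were watched for events. To 2 years that holds for the ODH arm. For controls it holds only as far as the chart was opened, was available and recorded the event. A control who joins the extension but declines chart review has no adverse event information for years 0 to 2. Nothing in the SAP removes that subject from the denominator, so the table cannot distinguish no event from not asked.

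Two figures are exposed. The control proportion is likely too low, which makes the ODH device look worse beside it. The pooled proportion is likely too low as well, which makes it look better than the ODH result. Long-term safety is a stated purpose of the extension, so readers will use both columns.

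**Working it through.** **Plan's own figures.** The documents give no adverse event rate, no capture rate and no sample size justification (SAP 5.1), so there is no derived figure to reproduce. The only arithmetic is 20 ODH + 5 controls = 25.

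**Is ascertainment really unequal?** The general adverse event row in the study schedule has no footnote limiting it to investigational subjects, which might suggest prospective collection in controls. Three places rule that out: protocol 22.3.1 (blood samples only), protocol 2.0 (not originally collected) and the control-only retrospective adverse event row, which stops at 2 years. From the 5-year visit onward the scheduled contacts are the same in both arms.

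**Inputs for the illustration.**
- Arm sizes 20 and 5: SAP 5.1.
- True proportion with an event, p, equal in both arms: assumed.
- Share s of control subjects with an event whom chart review identifies: assumed.

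**Formulas.**
- Control proportion shown = s × p
- Pooled proportion shown = p × (20 + 5s) / 25
- Ratio of ODH to control shown = 1 / s (true value 1)
- Relative understatement of the pooled rate = 1 − (20 + 5s)/25 = 0.2 × (1 − s)

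**Results at p = 0.40.**

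| s | ODH | Control | Ratio | Pooled | Pooled understatement (relative) |
|---|---|---|---|---|---|
| 1.0 | 40% | 40% | 1.00 | 40.0% | 0% |
| 0.9 | 40% | 36% | 1.11 | 39.2% | 2% |
| 0.7 | 40% | 28% | 1.43 | 37.6% | 6% |
| 0.5 | 40% | 20% | 2.00 | 36.0% | 10% |
| 0 | 40% | 0% | – | 32.0% | 20% |

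**Other values of p.** At s = 0.5, p = 0.20 gives 20% against 10% (pooled 18%), and p = 0.60 gives 60% against 30% (pooled 54%). The ratio and the relative understatement depend on s alone.

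**Consent alone.** If k of the 5 controls allow chart review, capture among them is complete and the denominator stays at 5, the expected pooled rate is multiplied by (20 + k)/25. That runs from 0.80 (k = 0) to 1.00 (k = 5).

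**An empty control column.** At p = 0.40 the chance that none of 5 controls shows an event is 0.6^5 = 7.8% with full capture and 0.8^5 = 32.8% with s = 0.5.

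**Sampling error.** The exact 95% interval is 0% to 52% for 0/5, and 19% to 64% for 8/20. The artefact adds to an already wide uncertainty.

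**The case against.** The case for leaving the SAP alone has real substance.

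- **The ODH result is already shown.** Reporting by treatment gives the ODH column, and control chart capture does not touch it. A reader might infer that the plan yields no usable safety figure; that is not so. This stands.
- **No comparison is planned.** SAP 6.9.2 names no test, difference or ratio for adverse events. Protocol 22.3.3 mentions Fisher's exact test for tables of counts in general, without tying it to adverse events. The harm is a misleading table, not a false p-value. This stands.
- **Protocol 22.3.1 is limited in scope.** A reader might infer that it bars any pooled column. The sentence excluding controls sits under the 2-year heading. The next subsection covers subjects completing the 5, 7 and 10 year visits and does not exclude controls. The reason given, that controls were asked only for blood, still applies to years 0 to 2, but the text does not prohibit pooling in the later analyses.
- **No text codes an unobserved control as event-free.** That is a consequence of reading the safety population literally, not a stated rule. The gap is a missing denominator rule. SAP 6.2 excludes retrospective-only subjects from the ITT set but is silent on them for the safety set.
- **Other outputs help.** Protocol 22.3.3 and 22.4 call for a time course of adverse events, 22.3.3 for a listing of all data, and SAP 6.6 for attendance at each visit. These allow partial separation by period, but none corrects the denominator.
- **Serious events may be well charted.** That is plausible for revisions and admissions, less so for mild events. It is a judgement; the documents give no figure.

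**Conclusion.** The point holds in a limited form. For surgery to 2 years the plan combines prospective and chart-review data on a primary endpoint, with no labelling and no denominator rule. The likely result is that the control and pooled proportions are too low. Direction is a judgement: the artefact vanishes only if chart review is complete for every control.

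The size cannot be known from the documents. On the assumptions of 40% true incidence in both arms and 50% to 90% capture, the control proportion falls by 4 to 20 percentage points and the pooled one by 0.8 to 4. A reader might take a pooled 32% (8/25) as the typical effect, but as an expected value it requires zero capture, so it is the extreme. The side-by-side reading carries the full artefact, while pooling dilutes it because controls are 5 of 25.

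The evidence also does not reach every pooled summary. The secondary endpoints in SAP 6.10 use the ITT set, which already excludes retrospective-only subjects, so removing the pooled column there does not follow from this point.

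**What to change.** Amend SAP 6.9.2 and the table shells:

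1. Tabulate adverse events in three periods that leave no gap:
   - surgery to 2 years: ODH prospective; control retrospective, shown separately and labelled as such;
   - after 2 years up to and including the 5-year visit: labelled in both arms as elicited at the 5-year visit, since no visit is scheduled in between;
   - after the 5-year visit: prospective in both arms.

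   Compare the arms side by side only in periods with the same ascertainment.
2. In either arm, count a subject in a period's denominator only if adverse event data were collected for that subject in that period. Show the number with data and the person-years.
3. Drop the pooled column from the adverse event tables, at least for surgery to 2 years, so that the ODH column is the safety result. A note should state how this relates to protocol 22.3.1.

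No new data are needed. The cost is slightly more table work and the loss of a single whole-study control or pooled proportion. The early control data lose no standing, because they are already only descriptive.

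### Adverse events other than device-related revision are summarised without time at risk, although contact intervals differ 12-fold and follow-up may differ between subjects

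*SAP*

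**What the plan says.** Adverse events are a primary endpoint (SAP 4.1) and are analysed in the safety population (SAP 6.9). SAP 6.2 defines that population as everyone enrolled and treated, whatever the length of follow-up.

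SAP 6.9.2 plans event totals and the "number and proportion of subjects experiencing an adverse event of any type", by treatment and overall, with breakdowns by seriousness, severity, relationship and outcome. For device effects over time it adds: "The frequency of ADEs and SADEs that occurred between each study visit will be presented along with the total for the overall study". It continues: "The number of subjects recording each will also be presented". No number under observation, person-time, rate or censored incidence is attached. Protocol 22.4 adds only a tabulated time course.

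On timing, Protocol 14.0 says "Subjects will be seen post-operatively at the 3 month, 6 month, 1, 2, 5, 7 and 10 year intervals, post-surgery", with "Telephonic assessment of adverse events at 6, 8 and 9 year intervals". For the primary study, Protocol 2.0 says "Patients will be followed-up for two (2) years post-operatively". For the extension, SAP 5.1 says "All patients completing the 2 year primary follow up were invited to participate in the extension phase of the study", and Protocol 2.0 and 5.1 require a new consent. Controls may agree to retrospective collection only (Protocol 2.0), and the SAP schedule ends their retrospective adverse-event collection at 2 years. Protocol 18.0 withdraws revised subjects from further visits.

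Device-related revision is handled differently: SAP 6.4 and 6.9.1 use Kaplan-Meier estimates with a stated censoring rule.

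**The concern.** Two separate problems follow from leaving out time at risk.

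- **Time course.** Counts per inter-visit row depend on the length of the row as well as on risk. Rows of very different length, shown side by side without a denominator, can make a steady risk look like a late rise, or hide a fall. The extension exists to assess the long-term safety of a new bearing, and this is the table a reader would use for that.
- **Cumulative incidence.** If some subjects are observed for about 2 years and others for 10, a proportion over everyone treated counts the unobserved years as event-free. That pulls long-term incidence down. If early stopping is more common in one arm, it can also create or hide a difference in the by-treatment display.

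**Working it through.** The documents state no adverse-event rate and no expected count, so there is no plan figure to reproduce. The check has three steps.

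**1. Interval lengths.** Inputs are the visit windows in the schedule of assessments (Protocol and SAP). Nominal day = lower window limit + allowance before the visit: 64+28=92, 155+28=183, 338+28=366, 689+42=731, 1812+14=1826, 2101+90=2191, 2466+90=2556, 2831+90=2921, 3196+90=3286, 3471+180=3651. (The printed 8-year upper limit, 3019, is not 2921+90=3011. Only lower limits are used here, so this has no effect.)

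Successive intervals are 92, 91, 183, 365 and 1095 days, then 365 days five times. Longest over shortest: 1095/91 = 12.03. The separate operation and discharge rows are left out.

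**2. Effect on the interval table.** Expected events = n × rate × days/365.25, with n = 20 ODH subjects, all under observation.

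- Constant rate, assumed 0.10 per patient-year: months 3–6 give 20×0.10×91/365.25 = 0.5; years 2–5 give 20×0.10×1095/365.25 = 6.0. The ratio of 12 does not depend on the assumed rate.
- Falling rate, assumed 0.20 then 0.05 per patient-year: months 3–6 give 20×0.20×91/365.25 = 1.0; years 2–5 give 20×0.05×1095/365.25 = 3.0. A fourfold fall in risk appears as a threefold rise in count.

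**3. Effect on a crude 10-year proportion.** Let r be a constant rate of first events and q the share observed for only 2 years. Neither is in the documents; both are assumptions.

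- Incidence under full follow-up: 1 − exp(−10r).
- Crude proportion over all treated: (1−q)(1 − exp(−10r)) + q(1 − exp(−2r)).

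For r = 0.05 the two terms are 1 − exp(−0.5) = 0.393 and 1 − exp(−0.1) = 0.095.

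| q | Crude proportion, r = 0.05 | Full follow-up | Crude/full, r = 0.02 to 0.10 |
|---|---|---|---|
| 0 | 0.393 | 0.393 | 1.00 |
| 10% | 0.364 | 0.393 | 0.92–0.93 |
| 25% | 0.319 | 0.393 | 0.80–0.82 |
| 50% | 0.244 | 0.393 | 0.61–0.64 |

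With q = 25% of 20 subjects, observed time is 15×10 + 5×2 = 160 of 200 patient-years.

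Between arms, with equal hazards (r = 0.05), if 3 of 5 controls have only 2 years and every ODH subject has 10, controls show 0.4×0.393 + 0.6×0.095 = 0.214 against 0.393.

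**The case against.** The strongest reply has five parts.

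- **Uptake is unknown.** A reader might infer that some of the 25 were in fact followed for only 2 years and that incidence is therefore understated. The documents say only that completers were invited. With complete follow-up the incidence bias is zero. This stands, and it limits the second problem to a possibility. It does not touch the first, which follows from the schedule alone.
- **The denominator is not settled.** A reader might infer that the ODH denominator stays at 20 throughout. SAP 6.2 and 6.9 point that way, but Protocol 22.3.1 describes the extension analyses as comprising subjects who completed the 5, 7 and 10 year visits. On that reading, subjects seen only to year 2 are not counted as event-free at year 10. The conflict is real and needs resolving.
- **Time at risk is not ignored everywhere.** Device-related revision has a censored analysis. SAP 6.6 tabulates visit attendance and reasons for discontinuation, Protocol 22.3.4 promises an accountability table, and Protocol 22.3.3 promises listings. With 25 subjects a reader could approximate denominators. It would be wrong to say that no planned figure uses follow-up. What remains is that none of this is linked to the adverse-event tables.
- **This is a descriptive pilot.** No adverse-event test is specified, row labels show that 2–5 years is long, and operation and discharge rows separate perioperative events. That lowers the stakes, but it does not supply a denominator.
- **Fine-grained rates would be uninformative.** Five controls over 3 months give 5×0.25 = 1.25 patient-years. With no events the exact 95% upper limit is 3.69/1.25, about 295 per 100 patient-years; for 20 ODH subjects it is 3.69/5, about 74. Poisson limits also treat repeat events in one subject as independent. This stands and shapes the remedy.

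**Conclusion.** The point holds for adverse events other than device-related revision.

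The time-course part is firm: with full follow-up, a constant risk yields about 12 times as many events in the 2–5 year row as in the 3–6 month row, whatever the rate.

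The incidence part is conditional. A crude proportion over the safety population may understate long-term incidence and may distort the by-treatment display. The relative shortfall is zero if everyone is followed to 10 years, about 18–20% if a quarter stop at 2 years, and about 36–39% if half do. These figures assume a constant first-event rate of 0.02 to 0.10 per patient-year. Stopping at exactly 2 years is a simplification, because revision, death and loss give intermediate times.

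The documents do not support the stronger claim that the reported incidence will be biased by a known amount.

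**What to change.** In SAP 6.9.2:

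1. Add to the ADE/SADE interval table, for each interval and arm, the number under observation and patient-years. Count years 2–5 only for subjects whose events in that period were ascertained.
2. Give events per 100 patient-years with an exact confidence interval for the overall period or a few broad periods by arm, not for every small cell.
3. Report first ADE and first SADE as 1 minus Kaplan-Meier at 6 months and 2, 5, 7 and 10 years, using the censoring rule already written for revision, beside the crude proportions. A device-related revision is itself recorded on the adverse-event form (Protocol 17.1 G), so the text should say how it counts in these curves.
4. State the adverse-event denominator at each analysis, reconciling Protocol 22.3.1 (visit completers) with the SAP safety population. Say whether controls with retrospective data only are included; the ITT definition excludes them and the safety definition does not.

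The cost is SAP wording and a few table columns, with no new visits. Intervals will be wide with 25 subjects. The censored estimate assumes that those who stop early carry the same later risk as those who continue. The case report form is not among the documents, so the sponsor should confirm that event onset dates are recorded.
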